In a single-center, randomized, double-blind, placebo-controlled, crossover pilot study, we will investigate the physiological effects and mechanisms of action of multiple forms of SCS (i.e., tonic 50 Hz, burst, tonic 1 kHz, sham) in 25 patients undergoing SCS. In this exploratory mechanistic study, we will evaluate the effects of somatosensory stimuli (e.g., vibration and pressure-pain stimuli) using static QST measures of sensory detection threshold, pain threshold, and/or tolerance to stimuli. We will assess dynamic central pain-processing mechanisms by measuring the perception of pain in response to sequential stimuli (temporal summation), and endogenous pain inhibition by measuring

pain sensitivity concurrent with the application of a conditioning stimulus (conditioned pain modulation). We will also obtain outcome measures to assess changes in pain intensity, pain quality, pain spread, and quality of life. We hypothesize that clinically effective forms of SCS will decrease temporal summation, reduce pain sensitivity, and improve conditioned pain modulation.

Interventions and Duration

Spinal cord stimulation (SCS) is a neuromodulation therapy used to treat medically refractory chronic pain. SCS systems are typically completely internalized systems that consist of two main components. The first component is an implanted pulse generator (IPG) that typically has a titanium casing and is most commonly implanted in the posterior hip area. The second component is electrode arrays consisting of 8-32 metal electrodes that are typically made out of platinum-iridium and implanted in the epidural space near the dorsal aspect of the spinal cord. There are two main types of SCS electrode arrays. The first type is cylindrical electrode arrays that can be implanted on an outpatient basis under local anesthesia using a Touhy needle. The second type of arrays is a paddle- or plate-style electrode array in which a surgeon performs a laminotomy for implantation. In SCS, the IPG generates short duration electrical pulses that are then applied to the tissues through the implanted electrode arrays. Subjects will be receiving SCS as part of their clinical care and study participation will be approximately 1-3 months in duration for each participant.

Sample Size and Population

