9.2 Sample Size and Randomization

The primary endpoint will be spinal cord stimulation (SCS)-induced changes in temporal summation (TS). We will calculate TS scores by subtracting the average pain rating of the single-stimulus trials from the average pain rating of the ten-stimuli trials (see Section 9.5.1). If the difference is a positive number, we will conclude that there was pain summation, where larger numbers will indicate increased pain summation or TS. If the difference is zero or a negative number, we will conclude that there was no pain summation or TS. As described in Section 3, we will consider four types or factor levels of SCS: Burst-SCS, KHFSCS, 50 Hz SCS, and Sham SCS. We will consider a repeated-measures design in which all four levels are tested in each participant. We will employ linear mixed-effects models in our analysis. Therefore, our null hypothesis will be that the group means with regards to TS are all equal. Our alternate hypothesis will be that the not all of the group means of TS are equal. If we can reject the null

hypothesis, we will perform the appropriate post-hoc analyses to determine specific differences. To determine specific treatment effects, we will perform the following pairwise tests: Burst vs. Sham, 1 kHz vs. Sham, and 50 Hz vs. Sham. These tests do not require an adjustment for multiplicity because they are hierarchical.

We will perform statistical analysis on SCS-induced changes in TS measured by differences in the corresponding TS. For our study, we assumed a sample size of 20 (25 recruited with an attrition rate of 20% that was estimated from prior SCS studies that employed a similar crossover study design^{39,41}), 80% power, and 5% level of significance with two-tailed tests. Using a paired t test, this will allow us to detect a within-subject effect size (i.e., standardized difference score, d_z) of 0.68, reflecting the difference between active and sham SCS. While this study is exploratory, in the most comparable study conducted to date, eight subjects with neuropathic pain underwent SCS.⁶¹ Assuming a correlation value of 0.5 between TS measured in the same subject, the d_z for the effects of “ON” versus “OFF” stimulation was 0.89. A similar effect size in our study will achieve a statistical power greater than 95% with a sample size of 20.

Treatment Assignment Procedures

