Visual analog scale (VAS). We will measure intensity of back pain, leg pain, and general pain using patient-reported ratings on the VAS. VAS ratings are the most commonly-used clinical outcome measure in SCS. Operationally, a VAS is usually a horizontal line, 100 mm in length, anchored by word descriptors at each end, such as “no pain” and “worst possible pain”. The patient marks on the line the point that they feel represents their perception of their current state. The VAS score is determined by measuring in millimeters from the left hand end of the line to the point that the patient marks. The main advantage of using VAS ratings is that it will allow us to compare our outcomes to other clinical results available in the literature.^{1,2,7-9,41,66}

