We will use the validated model to investigate the underlying mechanisms of pain relief induced by SCS. We will compare the model output (i.e., W population firing rate) on a patient-by-patient basis. We will also compare the model outputs predicted between the groups of responders versus non-responders. For patients who obtained successful pain relief with SCS, we will compare the model output for clinically effective stimulation parameters versus clinically ineffective stimulation parameters.

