Exploratory analyses: To investigate the anti-nociceptive effects of SCS, we are proposing to conduct an exploratory, mechanistic, placebo-controlled study in 25 patients undergoing SCS for chronic pain. We will use quantitative sensory testing (QST) to assess spinal and supraspinal pain processing. In addition to the primary outcome described in Section 9.4.2, we will perform several exploratory analyses. We will evaluate the effects of somatosensory stimuli using static QST measures of sensory detection threshold, pain threshold, and/or tolerance to stimuli (i.e., vibratory threshold, pressure-pain threshold). We will also assess dynamic central pain-processing mechanisms, such as endogenous pain inhibition, by measuring pain sensitivity concurrent with the application of a conditioning stimulus (i.e., conditioned pain modulation (CPM)).¹⁵ Furthermore, we will obtain outcome measures to assess changes in pain intensity, pain quality, pain spread, and quality of life. Additional exploratory outcomes will include patient-reported VAS ratings for back, leg, and general pain,^{1,2} and several self-reported patient questionnaires, such as the Short-Form McGill Pain Questionnaire to assess quality of pain,³ Michigan Body Map to quantify the degree of widespread body pain,⁴ EQ-5D to characterize quality of life,⁵ Pain Disability Index (PDI) to measure pain-related disability,⁶⁸ and questionnaires from the Patient Reported Outcomes Measurements Information (PROMIS)⁶. We will identify responders as patients who demonstrate a $\geq 50\%$ reduction in average pain intensity (as measured by the VAS) with active SCS as compared to sham stimulation, a standard criterion for success with SCS.²² We hypothesize that patients who respond to specific types of SCS will show decreased spinal segmental sensitivity, particularly decreased vibration sensitivity and pressure-pain sensitivity. We believe that effective SCS will also modulate dynamic central pain-processing mechanisms. We hypothesize that effective types of SCS (i.e., patients who show $\geq 50\%$ reduction in average pain intensity) will reduce TS (primary outcome) and improve inhibitor CPM.

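### The exploratory hypothesis linking TS and CPM to pain relief defines relief only by a ≥50% VAS cut in about 20 people, and no planned analysis uses the continuous VAS collected alongside them

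*Combined protocol and SAP*

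**What the plan says.** The Précis states the general hypothesis without a cut: "We hypothesize that clinically effective forms of SCS will decrease temporal summation, reduce pain sensitivity, and improve conditioned pain modulation". Sections 1.3 and 3 say much the same. None of the three defines clinically effective.

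Section 9.6 supplies the definition under its exploratory analyses. A responder has a VAS reduction of at least 50% on active stimulation relative to sham, and the hypothesis is restated in those terms: "We hypothesize that effective types of SCS (i.e., patients who show $\geq 50\%$ reduction in average pain intensity) will reduce TS (primary outcome"). The same paragraph expects lower vibration and pressure-pain sensitivity in responders and better inhibitory CPM with effective stimulation. It gives no test or model for these statements.

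Section 9.5.2, on the spinal circuit model, uses the same grouping: "We will also compare the model outputs predicted between the groups of responders versus non-responders". This is one of three comparisons there. The others are patient by patient, and between effective and ineffective settings within patients who obtained relief.

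The underlying measure is continuous: "The VAS score is determined by measuring in millimeters from the left hand end of the line to the point that the patient marks". The schedule in section 6.1 collects it with TS and CPM at every visit from Visit 2 to Visit 6.

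Section 9.1 models continuous VAS as an outcome compared across treatments. It also plans ≥50% VAS improvement as a binary outcome in a mixed-effects logistic model. The primary analysis (sections 9.2 and 9.6) compares mean continuous TS across the four treatments, with no responder split.

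**The concern.** Whether TS, CPM and static thresholds move with pain relief is a different question from whether mean TS differs between treatments. Mean TS could fall without tracking relief, or track it within people while the treatment means stay close. The plan approaches the first question only through the cut.

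The cut treats a 49% reduction like no reduction and separates 49% from 51%. Because it is a ratio to the sham score, a fall from 20 to 10 mm counts as a response, while a fall from 80 to 45 mm (35/80 = 44%) does not. Each person has up to three active treatments, and section 9.6 does not say how someone who responds to one but not another is grouped.

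With about 20 people, a comparison of responders and non-responders could well miss an association that the continuous data would show. A null result might then be read as evidence against TS, or against the circuit model, as a marker of SCS effect.

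**Working it through.** **1. The plan's own figure.** Section 9.2 sizes the primary contrast with "80% power, and 5% level of significance with two-tailed tests" and 20 evaluable participants: 25 × (1 − 0.20) = 20. For a paired t test with n = 20, exact noncentral-t power reaches 80% at d_z = 0.660. At the stated d_z of 0.68, power is 82.2% (80.0% with n = 19). At d_z = 0.89 it is 96.5%, which agrees with the stated figure above 95%. The sizing is sound to slightly conservative, and it involves no responder cut. The documents state no power for the responder question.

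**2. Information kept by the cut.** If the VAS change is normal and is cut so that a share p responds, the large-sample efficiency relative to the continuous score is φ(c)² / [p(1 − p)], where c is the normal quantile at the cut.

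- p = 0.58: 0.3909² / (0.58 × 0.42) = 0.1528 / 0.2436 = 0.63
- p = 0.30: 0.3477² / (0.30 × 0.70) = 0.1209 / 0.21 = 0.58
- p = 0.20: 0.2800² / (0.20 × 0.80) = 0.0784 / 0.16 = 0.49

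On this measure, 20 people analysed through the cut are worth about 0.63 × 20 = 12.5 people at a 58% share and 0.49 × 20 = 9.8 at 20%.

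**3. Power at n = 20.** Inputs:

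- n = 20 and two-sided 5%, from section 9.2.
- Responder share: section 2.1 gives about 58% for SCS generally, and 60% (burst) and 51% (conventional) from one trial. None is stated to be versus sham, so shares of 20% to 60% are shown.
- Correlation r between VAS change and TS change: not in the documents; 0.2 to 0.8 assumed. The 0.5 in section 9.2 is the correlation between TS measurements in the same subject, a different quantity.

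Bivariate normal changes versus sham were simulated with one active treatment per person, 40,000 runs per cell. A regression t test on continuous VAS was compared with a two-group t test of TS change by responder status. At a 58% share:

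| r | Continuous VAS | Responder cut | Loss (points) |
|---|---|---|---|
| 0.3 | 25% | 17% | 8 |
| 0.4 | 43% | 28% | 15 |
| 0.5 | 64% | 42% | 22 |
| 0.6 | 84% | 61% | 23 |
| 0.7 | 96% | 79% | 17 |
| 0.8 | 100% | 93% | 7 |

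Shares of 40% to 60% give nearly the same losses. At a 30% share the loss is 17 points at r = 0.4 and 28 at r = 0.6. At a 20% share it is about 21 and 38. Across r of 0.2 to 0.8 and shares of 20% to 60%, the loss runs from about 3 to 38 points.

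**4. More than one change per person.** Up to 20 × 3 = 60 active-versus-sham changes exist. Treating them as independent, which is an optimistic bound, the loss at a 58% share is 11 points at r = 0.2, 20 at 0.3, 18 at 0.4, 8 at 0.5 and 2 at 0.6.

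**The case against.** Much of the case on the other side stands. Section 9.6 specifies no test, so the two-group comparison priced above is a construction. The wording could equally mean an active-versus-sham contrast within responders, which was not simulated. The simulation also cuts a normal change score at a quantile, whereas the plan cuts percentage reduction from each person's sham score. The loss figures are therefore conditional illustrations. In section 9.5.2 the responder split is only one of three comparisons, and sections 1.3 and 9.6 also plan to correlate model predictions with experimental measurements. The cut has a stated reason and a cited source, which is enough for an exploratory definition.

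Three stronger readings are tempting, and the documents support none of them.

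- A reader might infer that the trial's main mechanistic test loses power. It does not: the primary test compares continuous TS across treatments, and the general hypothesis in the Précis carries no cut.
- A reader might infer that a fixed loss of 15 to 25 points is built into the plan. That needs a correlation and a versus-sham share that the plan does not give, and a test that it does not name.
- A reader might infer that nothing else depends on the responder outcome, so it could be dropped. Section 9.1 plans it as a binary outcome with its own model.

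What remains is the gap itself. No planned analysis relates TS, CPM or static QST to the amount of pain relief. Naming no test leaves this open and does not fill it.

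**Conclusion.** The point holds for the exploratory hypothesis in section 9.6 and for one circuit-model comparison in section 9.5.2. Both define effectiveness by the ≥50% cut alone, although continuous VAS is recorded alongside the sensory measures. The primary TS analysis and its sample size are untouched.

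The firmest figure is the information kept: about 63% at a 58% responder share and 49% at 20%, given approximate normality. The power loss is less certain because it also depends on the unknown correlation, and it would be small if that correlation is weak. The matter merits a change because the link between sensory measures and relief is close to the study's stated purpose and the data will already be in hand.

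**What to change.** In section 9.6, add a separate exploratory linear mixed model for each of TS, CPM and the static QST measures. The predictors are participant-mean VAS and participant-centred VAS (mm) for the same treatment period, with a participant random intercept. The centred term estimates the within-participant association with pain relief and uses every period. Fit the model with and without treatment: with treatment, the slope excludes association carried by mean differences between SCS types; without it, that part is seen. Name which VAS rating (back, leg or general) is used.

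Keep this apart from the primary TS model. VAS is measured after randomisation, and adding it there would make the active-versus-sham contrasts conditional on pain relief.

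In section 9.5.2, relate the modelled W firing rate to continuous VAS in the same way. Keep the ≥50% outcome and its logistic model in section 9.1. Show TS, CPM and model output by responder status as a supporting display, and state how a person who responds to only some treatments is grouped.

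The cost is wording and a few more exploratory models, with no new data, visits or participants. A slope per millimetre is also less familiar to SCS readers than a responder split.

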10. DATA COLLECTION AND QUALITY ASSURANCE

10.1 Data Collection Forms

All study related information will be collected via self-reported questionnaire as per the table below.

Form Name	Data Collection Method
Screening & Demographics	
Informed Consent	Study Coordinator / Team Member
Demographics	Participant
Socio-demographics	Participant
Concomitant Medications	Participant
Vitals (heartrate, blood pressure, respiration rate, blood temperature), height and weight	Clinical staff
Self-Report Patient Questionnaires	
Short Form McGill Pain Questionnaire (SFMPQ)	Participant
Pain Disability Index (PDI)	Participant
Brief Pain Inventory (BPI)	Participant
Michigan Body Map (MBM)	Participant
Fibromyalgia Survey Questionnaire (FSQ)	Participant
PainDETECT	Participant
Hospital Anxiety and Depression Scale (HADS)	Participant
Patient-Reported Outcomes Measurement Information System Sleep Disturbance	Participant
Short Form Questionnaire (PROMIS-SD)	
Coping Strategies Questionnaire (CSQ)	Participant
EQ-5D Health Questionnaire	Participant
Visual Analog Scale (VAS) – included in SFMPQ	Participant
Generalized Mechanical Sensitivity	
Multimodal Automated Sensory Test (MAST)	Participant / Study Coordinator / Team Member
Spinal Segmental Sensitivity	
Vibrometer Test	Participant / Study Coordinator / Team Member
Algometer Test	Participant / Study Coordinator /

PinPrick Test

Team Member
Participant /
Study Coordinator /
Team Member

Quantitative Sensory Testing (QST)

Conditioned Pain Modulation (CPM) Test

Participant /
Study Coordinator /
Team Member

Stimulator programming

Burst, 1kHz, 50Hz, Sham SCS

Participant /
Study Coordinator /
Team Member

Safety

Adverse Events

Study Coordinator /
Team Member

10.2 Data Management

The University of Michigan Division of Pain Research, Chronic Pain and Fatigue Research Center, and other study personnel will be responsible for the collection of all source information. All Case Report Forms will be approved by the University of Michigan IRB.

Participants will complete electronic surveys or paper-based questionnaires. Electronic questionnaires will be completed via the Qualtrics Research Core at the University of Michigan. Data will be verified and checked for completeness and initialed by the study coordinator or other team member prior to the completion of the visit. All data will be entered into a research database (REDCap) by the study team.

Study data will be collected and managed using REDCap electronic data capture tools hosted at University of Michigan. REDCap (Research Electronic Data Capture) is a secure, web-based application designed to support data capture for research studies, providing: 1) an intuitive interface for validated data entry; 2) audit trails for tracking data manipulation and export procedures; 3) automated export procedures for seamless data downloads to common statistical packages; and 4) procedures for importing data from external sources.

10.3 Quality Assurance

10.3.1 Training

All study team members are required to be certified by the University of Michigan Program for Education and Evaluation in Responsible Research and Scholarship (PEERRS). In addition, research staff are required to follow study specific operating procedures as documented in the Manual of Operations and approved by the study PI.

10.3.2 Quality Control Committee

There is no quality control committee for this study, however, the study team will perform internal quality management of study conduct, data collection, documentation and completion. An individualized quality management plan will be developed to describe quality management.

Quality control (QC) procedures will be implemented beginning with the data entry system and data QC checks that will be run on the database that will be generated. Any missing data or data anomalies will be communicated to the study team for clarification/resolution.

Following written Standard Operating Procedures (SOPs), the monitors will verify that the clinical trial is conducted and data are generated and collected, documented (recorded), and physiological effects of spinal cord stimulation for pain reported in compliance with the protocol, International Conference on Harmonisation Good Clinical Practice (ICH GCP), and applicable regulatory requirements.

The investigational site will provide direct access to all trial related sites, source data/documents, and reports for the purpose of monitoring and auditing by the sponsor, and inspection by local and regulatory authorities.

10.3.3 Metrics

All outcome measures will be assessed for quality. If an outcome's value is above or below the possible range for that outcome, the data will be flagged for review.

10.3.4 Protocol Deviations

Protocol deviations will be documented on the visit checklist at each visit by the study team member responsible for that visit. The study coordinator will review the deviation and report to the study team via the Deviations Tracking Log. Corrective Actions, if required, will be noted in the subject file and study documentation. Major protocol deviations that may adversely impact safety of participants, or impact integrity/validity of the data and minor protocol deviations as part of a pattern and/or suggesting a systemic problem in study conduct that potentially places subjects or others at a greater risk of harm than was previously known or recognized will be reported as an Other Reportable Information or Occurrences (ORIO) within seven days of becoming aware of the event or information. Minor protocol deviations that do not impact safety of participants or impact integrity/validity of the data – for example, schedule deviations, minor informed consent deviations (wrong version date, wrong expiration date, as long as the content is same) will be reported as part of scheduled continuing review.

11. PARTICIPANT RIGHTS AND CONFIDENTIALITY

11.1 Institutional Review Board (IRB) Review

The protocol, informed consent form(s), recruitment materials, and all participant materials will be submitted to the Institutional Review Board (IRB) for review and approval. Approval of both the protocol and the consent form must be obtained before any participant is enrolled. Any amendment to the protocol will require review and approval by the IRB before the changes are implemented to the study. In addition, all changes to the consent form will be IRB-approved; a determination will be made regarding whether a new consent needs to be obtained from participants who provided consent, using a previously approved consent form.

